### **Number of patients**

198 Informed consent forms are supposed to be signed and expected to yield at least 158 patients (79 x 2 groups (Ergoferon and Oseltamivir)) completing all the protocol procedures (withdrawal index 1,2).

### **Treatment**

#### ***Group 1***

**Name:** Ergoferon

**Active ingredient:** affinity purified antibodies to human interferon-gamma – 0.006 g\*, affinity purified antibodies to histamine – 0.006 g\*, affinity purified antibodies to CD4 - 0.006 g\*

*\* applied onto lactose as a mixture of three active water-alcohol solutions of the API diluted 100^12, 100^30, 100^50 times, respectively.*

**Excipients:** Lactose monohydrate, microcrystalline cellulose, magnesium stearate.

**Dosage:** Per os. Dose per administration - 1 tablet (without food) hold in the mouth until complete dissolution.

Dosing scheme: One dose every 30 minutes for the first 2 hours, followed by three more doses spaced regularly during the rest of the day. From day 2 to 5: 1 tablet 3 times a day.

**Dosage form:** Orally disintegrating tablets.

**Description:** White to off-white, circular, flat faced, beveled edge tablets, scored on one side. Each tablet is debossed with MATERIA MEDICA on the scored side and ERGOFERON on the other flat side.

**Storage conditions:** Store in a place protected from light at a temperature below 25°C. Keep out of the reach of children.

#### ***Group 2***

**Name:** Tamiflu

**Active ingredient:** Oseltamivir 75 mg (as oseltamivir phosphate 98.5 mg)

**Excipients:** Pregelatinized starch, povidone K30, croscarmellose sodium, talc, sodium stearyl fumarate.

**Dosage:** Per os, with or without food. Dosage scheme: Adult patients - 1 capsule (75 mg) twice daily. Treatment period - 5 days.

**Dosage form:** Capsules

**Description:** Hard, gelatinised capsules, size 2. Grey opaque body; light yellow opaque cap. Capsule contents - white to yellowish-white powder. The capsule is engraved with “Roche” (body) and “75 mg” (cap) in light blue ink.

**Storage conditions:** Store below 25°C. Keep out of the reach of children.

***Treatment period***

Ergoferon/Tamiflu® treatment period is 5 days.

***Observation period***

Overall the patient was observed in the study for 7 days (screening/randomization/prescription of treatment - Day 1, study therapy – days 1-5, follow-up – days 6-7).

***Basic therapy***

Throughout the study the patients may receive symptomatic therapy for influenza based on the treatment standards including detoxication agents, vitamins, antitussive drugs and expectorants, mucolytics, vasoconstrictive nasal drops, where applicable\* - antipyretics\*\* except for antiviral, antihistamine, immunomodulating and other drugs included into “Forbidden concomitant therapy”.

*\* Indications for antipyretic therapy:*

*Body temperature > 39°C in patients without complications and co-morbidities and > 38°C in patients with co-morbidities (congestive heart failure, hepatic, renal diseases; mental diseases, diabetes mellitus, history of convulsive syndrome).*

*Given that congestive heart failure, mental disorders, diabetes mellitus are exclusion criteria for this clinical study, these indications need not be considered.*

*If antipyretic product was administered by the patient on his/her own (without medical prescription) with no indications thereto the patient will not be withdrawn from the study. The patient should record thermometry values in the diary before the product administration as well as its name and dose.*

*\*\* Products approved as antipyretics (ATC group is specified in brackets):*

- 1. Paracetamol (N02BE01).*
- 2. Ibuprofen (M01AE01).*
- 3. Metamizole sodium (N02BB02) – for hyperthermia uncontrolled by paracetamol/ibuprofen as an emergency drug.*

The product shall be chosen by the investigator issuing the antipyretic to the patient at Visit 1.

***Prohibited concomitant therapy***

Within one month prior to enrollment\* and throughout the study (beginning with signing Informed Consent and initiation of screening) patients cannot use any of the following medications (ATC group is specified in brackets):

[figure not shown]
1. Antiviral drugs (J05) except for Ergoferon and oseltamivir prescribed within the study.

2. Immune sera and immunoglobulins (J06).
3. Vaccines (J07).
4. Antitumour drugs (L01) and antitumour hormonal products (L02).
5. Immunostimulants (L03) including:
  - Colony-stimulating factors (L03AA) – filgrastim, molgramostim, lenograstim, pegfilgrastim.
  - Interferons (L03AB) – interferon alpha, interferon gamma, interferon alpha-2a, interferon alpha-2b, interferon alpha-n1, interferon beta-1a, interferon beta-1b, peginterferon alpha-2b, peginterferon alpha-2a.
  - Interleukins (L03AC) – aldesleukin.
  - Other immunostimulants (L03AX) – BCG vaccine; pidotimod; glatiramer acetate.
  - Interferon inducers (acridonacetic acid, meglumine acridonacetate, complex of polyadenylic acid and polyuridylic acid, methylphenylthiomethyl-dimethylaminomethyl-hydroxybromindole carboxylic acid ethyl ether, oxodihydroacridinylacetate sodium, kagocel, tilorone).
  - The products containing thymus hormones (alpha-thymosin, alpha-glutamyl-triptophan, thymus extract, thymoptin).
  - B-activin.
  - Synthetic immunostimulants (levamisole, alpha-glutamyl-triptophan).
  - Bacterial immunomodulators (ribomunyl, ribonucleate sodium, deoxyribonucleate sodium)
6. Immunodepressants (L04).
7. Fenspiride (R03DX03), omalizumab (R03DX05).
8. Antihistamine drugs (R06).
9. Anaferon (L03AX), epigam, rengalin (R05DB).
10. Combined products for symptomatic therapy of acute respiratory diseases containing acetylsalicylic acid, diclofenac, propifenazone, metamizole, phenylephrine, H1-histamine blockers (including phenyramine, chlorphenamine).
11. Drugs known to have caused allergic reactions.
12. Products forbidden as antipyretic products:
  - Butylpyrazolidones (M01AA) including phenylbutazone.
  - Acetic acid derivatives (M01AB) including indometacin, diclofenac, ketorolac, aceclofenac.
  - Oxicams (M01AC) including piroxicam, meloxicam, tenoxicam, lornoxicam.

- Propionic acid derivatives (M01AE).
- Coxibs (M01AH).
- Niflumic acid (M01AX02).
- Nimesulide (M01AX17)
- Acetylsalicylic acid (N02BA01) including in combination with other products.
- Pyrazolones (N02BB) including in combination with other products (except for metamizole sodium).

*\* If a single dose of any of the products from the list “Forbidden concomitant therapy” was administered within 12 hours prior to the enrollment to the study (except for the products specified in cl. 2-4, 6), it is not an exclusion criteria.*

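### Ibuprofen is an approved antipyretic under Basic therapy, but item 12 of Prohibited concomitant therapy forbids its whole class as antipyretics, with no exception

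*Combined protocol and SAP*

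**What the plan says.** **Approval.** Basic therapy lists three permitted antipyretics with their ATC codes: paracetamol (N02BE01), "Ibuprofen (M01AE01" and metamizole sodium (N02BB02). Metamizole is reserved "for hyperthermia uncontrolled by paracetamol/ibuprofen as an emergency drug", which places ibuprofen beside paracetamol as a first choice. The section adds: "The product shall be chosen by the investigator issuing the antipyretic to the patient at Visit 1".

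**Prohibition.** Item 12 of Prohibited concomitant therapy is headed "Products forbidden as antipyretic products". It includes the line "Propionic acid derivatives (M01AE", which carries no exception. The pyrazolone line of the same item does carry one: "except for metamizole sodium". The list applies "Within one month prior to enrollment" and throughout the study. A footnote excuses a single dose of most listed products, item 12 included, if it "was administered within 12 hours prior to the enrollment to the study".

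**Rules that refer to the list.** Exclusion criterion 15 bars use of a listed medicine in the 30 days before inclusion. Discontinuation criterion 3 is the need for a drug the study does not permit, and criterion 7 is an eligibility error. Under Statistical Analyses, Samples, the Full Analysis Set drops patients who fail the entry criteria, and the Per Protocol set drops those with major deviations.

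**The concern.** Both entries concern the same use, fever reduction, and both rely on the protocol's own ATC codes. An investigator who issues ibuprofen on Day 1 follows one section and breaches the other.

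What is at stake is patient status. The forbidden list feeds eligibility, discontinuation and membership of both efficacy sets, so a drafting slip in it can reach the analysis populations. The trial is open-label, and the document describes no blinded review of such decisions. A rule open to two readings is better settled before anyone has to apply it to an individual patient.

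**Working it through.** No arithmetic applies and the plan gives no figure to reproduce. The check compares the two lists by ATC code and then follows the rules that depend on them.

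**Step 1. Approved products against item 12.**

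| Approved antipyretic | Code | Group listed in item 12? | Excepted there? | Result |
|---|---|---|---|---|
| Paracetamol | N02BE01 | No | Not needed | Consistent |
| Ibuprofen | M01AE01 | Yes, M01AE | No | Conflict |
| Metamizole sodium | N02BB02 | Yes, N02BB | Yes | Consistent |

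One of three approved products conflicts, and one of the two that come before metamizole. Elsewhere the drafter did write exceptions: item 1 excepts the two study drugs from the antivirals, and item 12 excepts metamizole. Ibuprofen is the only approved antipyretic in a listed group without one, so this looks like an omission.

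**Step 2. Does either section prevail?** No sentence says that the approved list overrides the forbidden list. The opening sentence of Basic therapy points the other way: it allows symptomatic treatment, antipyretics included, apart from drugs on the forbidden list. Basic therapy also speaks only of treatment during the study. A reader who lets it prevail on study therefore still has no text that clears ibuprofen taken for fever before enrollment.

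**Step 3. Consequences if the ban is applied literally.**

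- *On study.* Ibuprofen is a non-permitted drug. Needing it could meet discontinuation criterion 3, or its use could be classed as a major deviation and remove the patient from the Per Protocol set.
- *Before enrollment.* Ibuprofen taken for fever in the prior 30 days breaches exclusion 15, unless it was a single dose within the last 12 hours. If this is found after enrollment, it is an eligibility error (discontinuation criterion 7). It also removes the patient from the Full Analysis Set, taking that set's non-inclusion criteria to mean the exclusion criteria.
- *Use for another reason*, such as pain, is not clearly caught, because item 12 forbids these products as antipyretics.

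**Step 4. Size.** The document gives neither the share of patients expected to be issued ibuprofen nor the share taking it for fever beforehand. No count of affected patients can be derived.

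**The case against.** The best reply is that a named, coded and repeated permission is normally read ahead of a generic class heading. Ibuprofen appears in the approved list and again in the metamizole condition, and the investigator hands the product out. Sites would probably follow the approval. Calling a product issued in this way a major deviation would be strained. Basic therapy also states that a patient who takes an antipyretic unprompted and without indication is not withdrawn, which suggests leniency.

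The Full Analysis Set route needs several things to go wrong together: the literal ban is enforced, ibuprofen was taken for fever within 30 days outside the single-dose relief, the Day 1 checks of history, medicines and eligibility missed it, and it came to light later. Finally, the document calls itself a protocol summary. Whether a fuller protocol or site manual carries the exception cannot be checked.

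Most of this stands as a limit on practical effect. It does not remove the contradiction: the text does not give the approval priority, and the leniency rule concerns indication, not product, eligibility or analysis sets.

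A reader might go further and infer that every patient given ibuprofen must be withdrawn, or that the non-inferiority comparison is biased or loses power. The document supports neither inference. The first ignores the express approval. The second would need usage rates and a difference between arms, and the text gives neither. Setting the 48-hour presentation limit against the 12-hour relief does not size the problem either: that gap is common to every product the relief covers, and it counts no patients.

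**Conclusion.** The point holds as an internal inconsistency that is wrong as written; it is not a disputed design choice. The contradiction itself is certain from the wording. That the intent was to allow ibuprofen is an inference, though a strong one.

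Its size is one of three approved antipyretics. The effects on discontinuation, eligibility and the analysis sets are conditional on the ban being enforced literally, and their frequency is unknown. The correction is still worth making, because the literal rule gives a wrong result and costs almost nothing to repair.

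**What to change.** Change the item 12 line to read: *Propionic acid derivatives (M01AE), except for ibuprofen (M01AE01)*. This follows the form already used for metamizole. It takes ibuprofen off the forbidden list for exclusion 15, discontinuation criteria 3 and 7, and both efficacy sets at once. Send sites a short notice.

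If patients are already enrolled, apply the same reading to all of them in both arms, before the analysis sets are fixed and without reference to arm or outcome. That condition matters because the trial is open-label and the change could alter a patient's status retrospectively.

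The cost is one amendment line and one site notice. Sample size, endpoints and analysis methods do not change.

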### Study design scheme

### Schedule of study procedures

Procedure/visit	Day 1	Day 3	Day 5	Day 7
Obtaining informed consent (signing informed consent by the patient)	+			
Collection of complaints	+	+		+
Collection of medical history data	+			
Objective examination	+	+		+
Recording influenza symptoms in scores	+	+		+
Collection of nasal swabs and isolation of influenza agent antigens	+			
Collection of nasopharyngeal swab for PCR diagnosis	+	+	+	+
Pregnancy test	+			
Information on concomitant medicines	+	+		+

Inclusion/exclusion criteria	+			
Randomization and prescription of study therapy	+			
Antipyretic drug dispensing	+			
Blood sampling for immunological tests	+	+		+
Dispensing of the study drug	+			
Drug accountability and return, assessment of compliance				+
Distribution of diaries	+			
Evaluation of correct diary filling		+		+
Diary return				+
Evaluation of therapeutic safety		+		+

## Statistical Analyses

### *Samples*

Total set comprised all enrolled patients whose parents/adopters had signed the informed consent form for participation of a patient in the trial. This sample will consider all adverse events throughout the study, including those occurred prior to the study therapy. Any medically unfavourable events (conditions) recorded in patients from Total set after signing informed consent but before administration of the study product will be considered as concomitant conditions.

Sample of the patients receiving at least one dose of the study product will be used for the study drug safety assessment (Safety population), as any adverse events emerging after administration of the product will be recorded.

Full Analysis Set This sample will consist of all enrolled patients, except for those who met at least one of the following criteria:

- 1) failure to meet inclusion/non-inclusion criteria;
- 2) patient failing to take any dose of the study drug;
- 3) absence of any data on the patient after randomization.

This was the best set for the Intention-to-treat method, so it will be used in the Intention-to-treat efficacy analysis of the test therapy.

Unavailable/missing data (parameters/variants) will be completed by the Last Observation Carried Forward method (LOCF).

Per Protocol set. This sample includes all patients who completed the therapy as per the study protocol, without any missing visits or major protocol deviations. This set will be used in the Per Protocol efficacy analysis of the test therapy.

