### *Secondary Outcome Measures*

2. Fever changes over time (body temperature change on days 2-7 compared to baseline).
3. Average duration of fever.
4. Proportion of subjects with normal body temperature (below 37,0^0C) on days 2-7.
5. Severity of clinical manifestations of influenza (fever, general symptoms and nasal/throat/chest symptoms) in scores on day 1-7 – according to the patient's diary; on days 1, 3 and 7 – according to objective examination by the investigator.

---

 **Recovery criteria:** body temperature <37.0^0C + no symptoms.

**Improvement criteria:** body temperature ≤37.2C + total symptom score (except for fever index) ≤2 scores.

 Criteria of no fever - body temperature lower than 37.0° C for 24 hours.

6. Duration of the major clinical symptoms of influenza (fever, general symptoms and (nasal/throat/chest symptoms) in days (according to the patient diary).
7. Severity of influenza course (based on area under curve for total influenza severity score on days 1-7 – according to the patient diary; on days 1, 3 and 7 – according to objective examination by the physician).
8. Proportion of patients, who used antipyretics on days 1, 2, 3, 4 and 5 of the treatment.
9. Proportion of patients with complications requiring antibiotics, aggravation of the disease (severe influenza).
10. Proportion of patients with negative results of virology assay on days 3, 5 and 7 (based on PCR of nasopharyngeal swabs).
11. Dynamics of Parameters of Immune Status (T-cell and B-cell Immune Response) on days 1, 3 and 7 of the observation:
  - Concentration of regulators of the T-cell immune response (IL2, IFN  $\gamma$ , IL-18), and regulators of B-cell immune response (IL-4, IL-16).
12. Dynamics of Parameters of Immune Status ( IFN- $\alpha$  and IFN- $\gamma$  Production) on days 1, 3 and 7 of the observation:
  - Level of spontaneous and induced production of IFN- $\alpha$  and IFN- $\gamma$  by leukocytes (in vitro).
13. Dynamics of Parameters of Immune Status (Absolute Number of Each Type of White Blood Cells and Different Lymphocyte Phenotypes) on days 1, 3 and 7 of the observation:
  - The absolute number of each type of white blood cells (WBC): Absolut Count (AC) of leukocytes, neutrophils, lymphocytes, monocytes, eosinophils, basophils, and CD3, CD4, CD8, CD4/CD8, CD16, CD119 leukocytes.

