At Day 1, Day 3 and Day 7 visits blood sampling will be made for immunological tests at the investigator's discretion. At Day 3 and Day 7 visits the investigator will collect complaints, document examination findings, intensity of influenza symptoms in scores, control the prescribed and concomitant medications, assess safety of the study therapy and check the patient's diary. Furthermore, nasopharyngeal swabs (Days 1, 3, 5, 7) and blood samples (Days 1, 3, 7) will be made for lab tests. The total observation period will be 7 weeks (screening, randomization – 1 day, treatment – 5 days, follow-up – 2 days). The patient will keep diary throughout the whole 7-day observation period.

Symptomatic therapy of influenza and co-morbidities will be allowed except for the products specified in “Forbidden concomitant therapy” section.

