### **Discontinuation criteria**

1. Participant's failure or decline to comply with the protocol requirements.
2. Deviation from the schedule of examinations and sampling for lab tests by  $\geq 1$  day.
3. The necessity to use medications not permitted in the study.
4. An adverse event requiring discontinuation of the study drug.
5. Patients who decide to withdraw early from the study due to lack of treatment efficacy or for any other reason.

6. Cases not stipulated in the protocol where the investigator decides that further participation may harm the patient.
7. Eligibility error.

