### *Evaluation of sample size*

The sample size was assessed in accordance with the following rules and assumptions:

1. Statistical assumptions:

- 1.1 Lack of clinically relevant superiority of reference product (oseltamivir) over test product (Ergoferon) is assumed, thus statistically meeting Non-Inferiority design:

$$\mathbf{H_0: Ef_{control} - Ef_{test} \geq \delta}$$

$$\mathbf{H_A: Ef_{control} - Ef_{test} < \delta,}$$

where  $\mathbf{Ef_{control}}$  – effect of reference product (oseltamivir),  $\mathbf{Ef_{test}}$  – effect of test product (Ergoferon),  $\delta$  – clinically relevant difference;

- 1.2 Clinically relevant difference value “ $\delta$ ” is considered to be equal to 20% (i.e. Ergoferon effect is supposed to be comparable to the one of oseltamivir if the effect of test product is superior to or inferior to the effect of reference product by no more than 20%);
- 1.3 The power of statistical tests ' $P = (1 - \beta)$ ' is 80% (the probability of correct rejection of the null hypothesis is 0.8);
- 1.4 The probability of type 1 error ' $\alpha$ ' is less than 5% (the probability of false acceptance of the alternative hypothesis is less than 0.05);
- 1.5 Therefore, sample size will be calculated taking into account:
- a. assumption on expected effects declared in the main efficacy criterion of the protocol;
- 1.6 calculation of sample size of groups 1 and 2 for two-sided test for final analysis will be made using the formula:

$$\mathbf{N_1=N_2=(p_a(1 - p_a) + p_b(1 - p_b)) I,}$$

where  $\mathbf{N_1}$  and  $\mathbf{N_2}$  – samples sizes in Ergoferon and Oseltamivir groups

$\mathbf{p_a}$  and  $\mathbf{p_b}$  – expected proportions of the patients with recovery/improvement in these groups

$\mathbf{I}$  – Fisher's information detected using the formula:

$$\mathbf{I=(z_\alpha + z_\beta)^2/(\theta - \delta)^2,}$$

where  $\mathbf{z_\alpha}$  and  $\mathbf{z_\beta}$  – tabular values of z-test for  $\alpha$  and  $\beta$ ,  $\theta$  – difference between proportions ( $\mathbf{p_a - p_b}$ ),  $\delta$  – clinically relevant difference;

- 1.7 final sample size will be determined using the formula:

$$\mathbf{N_F = N / (1 - K_B),}$$

---

 SAS/STAT(R) 9.2 User's Guide, Second Edition.

[http://support.sas.com/documentation/cdl/en/statug/63033/HTML/default/viewer.htm#statug\\_seqdesign sect027.htm](http://support.sas.com/documentation/cdl/en/statug/63033/HTML/default/viewer.htm#statug_seqdesign sect027.htm)

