**Parametric criteria**

Prior to analysis using parametric statistics, data samples under comparison will be tested for normality (the Kolmogorov-Smirnov test).

 **Recovery criteria:** body temperature  $<37.0^{\circ}\text{C}$  + no symptoms.

**Improvement criteria:** body temperature  $\leq 37.2^{\circ}\text{C}$  + total symptom score (except for fever index)  $\leq 2$  scores.

The following parameters and approaches are to be used:

1. To evaluate the differences in continuous variables from two different (independent) groups – Student’s test for independent samples.
2. To evaluate differences in continuous variables in one group at two different visits - Student’s test for paired samples.
3. To evaluate time changes in parameters compared - analysis of variance (ANOVA) or modified repeated measures covariance (ANCOVA).
4. In case of multiple comparisons of the groups various corrections for multiplicity will be used, e.g. Dunnett, Tukey, Scheffe, Holm adapted test, etc.
5. In case of abnormal data distribution generalized linear models and/or mixed linear models will be used.
6. Selection of the type of distribution, specification of factor and covariance structures of the model will be made using fit-statistics such as AIC (Akaike information criterion).

The following SAS software programs are supposed to be applied to the above listed tests and techniques:

- UNIVARIATE: normality verification of the distributions under comparison
- CORR, MEANS - calculation of descriptive statistics
- TTEST – Student’s test with all modifications
- GLM – generalized linear models for analysis of time changes (ANOVA, ANCOVA)
- GENMOD – generalized linear models
- MIXED – mixed linear models.

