***Non-parametric tests:***

Below are potential types of comparisons with relevant criteria:

1. To evaluate difference in continuous variables obtained in two different (independent) groups – Mann-Whitney test.
2. To evaluate time changes in the parameters compared – Friedman test, nonparametric analogue of repeated measures analysis of variance.
3. For frequency analysis of contingency tables  $2 \times 2$  –  $\chi^2$  (if the frequency under comparison  $> 5$ ) or exact Fisher’s test (if one of the frequencies under comparison  $< 5$ ).
4. Cochran-Mantel-Haenszel test (modified  $\chi^2$  test for multiple comparisons) – to perform frequency analysis based on independent strata.
5. For frequency analysis of data on presence/absence of an event or outcome during repeated measurements (contingency tables with dependent strata) – survival analysis.

To perform the above-mentioned nonparametric statistical analysis the following SAS procedures are to be used:

- FREQ – Friedman test,  $\chi^2$  test and/or exact Fisher's test; Cochran-Mantel-Haenszel test.
- LIFETEST – survival analysis.
- NPAR1WAY - Mann-Whitney test.

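### LOCF is the only stated rule for filling missing data on a daily recovery status in an open-label non-inferiority trial, and it distorts the comparison when withdrawal differs by arm

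*Combined protocol and SAP*

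**What the plan says.** **Missing data.** Under Samples, the Full Analysis Set paragraph gives one imputation rule: "Unavailable/missing data (parameters/variants) will be completed by the Last Observation Carried Forward method (LOCF"). No sensitivity analysis accompanies it. The only other handling is exclusion. Patients with no data after randomisation leave the Full Analysis Set, and the Per Protocol set is restricted further: "This sample includes all patients who completed the therapy as per the study protocol, without any missing visits or major protocol deviations". The first set serves the intention-to-treat analysis and the second the per-protocol analysis. Neither is named as deciding non-inferiority.

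**Primary outcome.** Recovery/improvement is assessed on diary days 2-7 and by the physician on days 3 and 7 (Primary Outcome Measure).

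**Leaving the study.** The Discontinuation criteria include withdrawal for lack of efficacy or any other reason, need for a non-permitted medicine, non-compliance, and "Deviation from the schedule of examinations and sampling for lab tests by" one day or more. Study design says "The patient will keep diary throughout the whole 7-day observation period", but no text covers the days after discontinuation. The Schedule of study procedures has no early-withdrawal visit and returns the diary on Day 7 only.

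**Other methods listed.** Parametric criteria, item 5: "In case of abnormal data distribution generalized linear models and/or mixed linear models will be used". Non-parametric tests, item 5, offers survival analysis: "For frequency analysis of data on presence/absence of an event or outcome during repeated measurements (contingency tables with dependent strata". Neither is tied to missing data or to the primary outcome.

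**Antipyretics.** Recovery needs a temperature below 37.0 °C and no symptoms. Improvement needs at most 37.2 °C and "total symptom score (except for fever index) ≤2 scores". Neither definition mentions antipyretic use. The diary takes morning and evening readings, and Basic therapy asks for a reading before a dose. Antipyretic use on days 1-5 is secondary outcome 8.

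**The concern.** A day 3 status is a poor stand-in for day 7 when most patients recover in between. An early leaver frozen as not recovered stays a failure, and one frozen during a transient good day stays a success. If the arms lose patients at different rates, the arm with more early leavers is usually marked down more. In a non-inferiority comparison, extra loss on oseltamivir can manufacture non-inferiority and extra loss on Ergoferon can hide it.

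The trial is open-label, so a patient's or investigator's view of the assigned drug can influence who leaves. The Per Protocol analysis does not repair this, because it drops patients with missing visits. With no deciding set named, two differing results could be read either way after the fact.

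**Working it through.** **The plan's own figures.** 158 / (1 - 0.20) = 197.5, so 198 consents, or 99 per group; this reproduces. The 79 per group cannot be reproduced without an assumption, because no expected success rate is given. With a 20-point margin, zero difference and 80% power, one-sided 5% at a 50% rate gives 78, and two-sided 5% gives 79 at a rate of about 72.5%. Evaluation of sample size, item 1.6, refers to a two-sided test ("calculation of sample size of groups 1 and 2 for two-sided test for final analysis will be made using the formula"), so z = 1.96 is used below.

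**Decision rule.** Non-inferiority is declared if (p_O - p_E) + 1.96 × sqrt[p_O(1 - p_O)/79 + p_E(1 - p_E)/79] < 0.20, where O is oseltamivir, E is Ergoferon and the p are observed proportions. Error rates come from exact binomial enumeration.

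**Assumed rates (none is in the documents).** Day 7 success is 90% (O) vs 70% (E), so the true deficit sits at the margin. Day 3 success is 30% vs 15%. A proportion w withdraws and is frozen at day 3. Day 7 is used for illustration; the plan names no deciding day.

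LOCF day 7 rate = p7 × (1 - w) + p3 × w

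| w (O, E) | LOCF rates (O, E) | Gap | False non-inferiority |
|---|---|---|---|
| 0, 0 | 0.900, 0.700 | 0.200 | 2.7% |
| 10%, 10% | 0.840, 0.645 | 0.195 | 3.1% |
| 20%, 20% | 0.780, 0.590 | 0.190 | 3.5% |
| 15%, 5% | 0.810, 0.6725 | 0.1375 | 15.0% |
| 5%, 15% | 0.870, 0.6175 | 0.2525 | 0.3% |

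For example, in the 15%/5% row: O = 0.90 × 0.85 + 0.30 × 0.15 = 0.810; E = 0.70 × 0.95 + 0.15 × 0.05 = 0.6725.

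**Sensitivity to the assumptions.** With assumed day 3 pairs of 20/10, 40/30, 50/30 and 60/45%, equal withdrawal of 10-20% gives 2.6-4.8%, and the 15%/5% case gives 7.4-19.2%. With 99 per arm instead of 79, the 15%/5% case gives 17.6%.

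**Daily leaving rather than a single freeze.** Assume a two-state daily chain with success on days 2-7 of 10, 30, 50, 70, 82, 90% (O) and 5, 15, 30, 45, 60, 70% (E), and daily relapse of 3%. Patients may leave after any of days 2-6, and unrecovered patients leave three times as often as recovered ones.

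- *The same leaving rule in both arms.* At mean withdrawal of 10-20% the LOCF gap is 0.196-0.191 and false non-inferiority is 3.0-3.4%. At mean withdrawal of 5% it is 2.8%.
- *Total withdrawal forced equal by arm (10-20%).* The result is 4.1-5.7%. Fewer Ergoferon patients are recovered in this chain, so equal totals require unrecovered oseltamivir patients to leave faster: 0.031 vs 0.026 per day at 10%, and 0.065 vs 0.055 at 20%.

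**Failure-scoring is not a safe alternative.** Scoring every withdrawal as a failure gives 0.81 vs 0.63 (gap 0.18) at equal 10% and 0.72 vs 0.56 (gap 0.16) at equal 20%, with error rates of 4.8% and 7.6%.

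**Antipyretic days.** Take an assumed mid-course day of 60% vs 40%, with a base error of 2.4%. Counting 10% or 20% of successes in each arm as failures, because an antipyretic was taken, gives 0.54 vs 0.36 or 0.48 vs 0.32. The error rates are 4.2% and 7.1%.

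**The case against.** **Equal withdrawal.** A reader might infer that LOCF inflates the error materially even when both arms lose the same share, citing 4.1-5.7%. That does not follow, because those figures contain a hidden arm difference in leaving rates. Under one common rule the error stays near its no-withdrawal level.

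**Direction.** A reader might also infer that LOCF always favours non-inferiority. It does not: the reversed imbalance gives 0.3%, which would conceal true non-inferiority.

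**Amount of withdrawal.** The 20% in Evaluation of sample size covers losses during screening as well as during the study. Loss after randomisation over seven days is therefore probably lower, and a 15% vs 5% split is an illustration, not a forecast. This stands.

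**Silence in a summary.** The document calls itself a protocol summary, so follow-up after discontinuation may be described elsewhere. The documents support saying that the rule is not stated here. They do not support saying that follow-up stops.

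**Antipyretics.** The success definition also limits symptoms, doses are recorded, a pre-dose reading is requested and use is a secondary outcome. Most of the needed data would therefore exist. A reader might infer a known inflation from antipyretic masking, but the documents give no figure for any such effect. What remains is that no rule says which reading classifies the day.

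**Conclusion.** The point holds as a problem of withdrawal that differs by arm. LOCF is the sole imputation rule for a status that changes daily, outcome-related withdrawal is allowed for, and the open-label design cannot exclude an imbalance. Under the assumed rates, a ten-point imbalance moves false non-inferiority from 2.7% to 15% or 0.3%, depending on the arm. With other assumed day 3 rates the upper figure ranges from 7.4% to 19.2%.

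With a common leaving rule LOCF does little harm in the daily-chain model. The antipyretic gap is secondary and its size is unknown. The unnamed deciding set is a missing specification that leaves room for choice after the data are seen. The change should be made before analysis, since the daily diary already provides the data for a better method.

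**What to change.** 1. **Follow-up.** State that patients who stop study treatment continue the diary and the Day 7 assessment if they agree, and that these observations, including off-schedule ones, enter the Full Analysis Set. Reconcile this with the Discontinuation criteria, which speak of leaving the study and list schedule deviations. The criteria themselves need not change for this purpose.
2. **Primary method for days still missing.** Replace LOCF by multiple imputation, separately by arm, of daily temperature and symptom score, or by a likelihood-based mixed model. Unweighted GEE through the listed GENMOD procedure is not suitable, because it is not generally valid when leaving depends on recorded status. The proposed methods assume that leaving depends only on recorded data, so add a tipping-point analysis that lowers imputed Ergoferon success. Keep LOCF as a sensitivity analysis.
3. **Deciding set.** Name it in advance. If both sets must show non-inferiority, state that power is below that of either alone.
4. **Antipyretic days (secondary).** State which reading scores the day, for example the highest recorded that day including pre-dose readings. Confirm that pre-dose readings cover prescribed as well as self-administered doses. Add a sensitivity analysis counting antipyretic days as not recovered, with the note that it is not conservative for non-inferiority.

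**Cost.** An imputation model to specify, some handling of off-schedule data, one diary instruction and a little more analysis. The planned number of patients need not change, unless both sets are required and the lost power is to be recovered.
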